6.6. Dose Modification

Patients will be initiated on ALXN1840 at 15 mg once daily, then the dose will be increased to 30 mg once daily at Week 6 (Day 43).

The dose should be decreased or interrupted if any of the relevant Dose Modification Criteria are met (see [Table 6](#)). Deviation from the dose modification guidelines must be agreed with the Alexion Medical Monitor. Any subsequent dose increases must be approved by Alexion.

All patients will continue to be treated with ALXN1840 in the Extension Period at the same dose they received at the last study visit in the Treatment Period and ALXN1840 administration during the Extension Period will follow the same procedures as for the Treatment Period.

In case a dose modification is necessary for ALXN1840, it will be administered as per the details in [Table 6](#).

Table 6: ALXN1840 Dose Modifications for Individual Patients

Test	Result	Conditions	Action with ALXN1840 Dosing	Changes in Safety Monitoring ^a	Re-Challenge ^b
ALT	> 5 × ↑ from baseline	ALT above reference range at baseline	Temporary interruption	Contact patient within 48 hours to arrange repeat testing Weekly repeat testing	At 15 mg QOD when ALT < 2 × ↑ from baseline.
	> 5 × ULN	ALT within reference range at baseline	Temporary interruption	Contact patient within 48 hours to arrange repeat testing Weekly repeat testing	At 15 mg QOD when ALT < 2 × ULN.
	> 2 × ↑ from baseline	ALT above reference range at baseline	Reduce dose to previous dose level if up-titration has occurred or reduce dose to 15 mg QOD if on 15 mg QD. No further dose ↑ until resolution of abnormality.	Weekly repeat testing	Not applicable.
	> 2 × ULN	ALT within reference range at baseline	Reduce dose to previous dose level if up-titration has occurred or reduce dose to 15 mg QOD if on 15 mg QD. No further dose ↑ until resolution of abnormality.	Weekly repeat testing	Not applicable.
Increased triglycerides	> 300 to 500 mg/dL or > 3.4 to 5.6 mmol/L	None	Reduce dose to previous dose level if up-titration has occurred or reduce dose to 15 mg QOD if on 15 mg QD. No further dose ↑ until resolution of abnormality.	Weekly repeat testing	Not applicable
	> 500 mg/dL or 5.6 mmol/L		Temporary interruption		At 15 mg QOD when triglyceride concentrations return to baseline
Increased total cholesterol	> 300 to 400 mg/dL or > 7.8 to 10.3 mmol/L	None	Reduce dose to previous dose level if up-titration has occurred or reduce dose to 15 mg QOD if on 15 mg QD. No further dose ↑ until resolution of abnormality.	Weekly repeat testing	Not applicable
	> 400 mg/dL or > 10.3 mmol/L		Temporary interruption		At 15 mg QOD when cholesterol concentrations return to baseline

Test	Result	Conditions	Action with ALXN1840 Dosing	Changes in Safety Monitoring^a	Re-Challenge^b
Hemoglobin	< 8 g/dL in the absence of bleeding	None	Temporary interruption	Weekly repeat testing	At 15 mg QOD when hemoglobin and other hematology parameters (neutrophils and platelets) are at baseline concentration.
	> 30% ↓ from baseline	None	Reduce dose to previous dose level if up-titration has occurred or reduce dose to 15 mg QOD if on 15 mg QD. No further dose ↑ until resolution of abnormality.	Weekly repeat testing	Not applicable.
Platelets	< 30,000/μL	None	Temporary interruption	Weekly repeat testing	At 15 mg QOD when platelets and other hematology parameters (neutrophils and hemoglobin) are at baseline concentration.
	> 30% ↓ from baseline	Platelets below reference range at baseline	Reduce dose to previous dose level if up-titration has occurred or reduce dose to 15 mg QOD if on 15 mg QD. No further dose ↑ until resolution of abnormality.	Weekly repeat testing	Not applicable.
Neutrophils	< $1.0 \times 10^3/\mu\text{L}$	None	Temporary interruption	Weekly repeat testing	At 15 mg QOD when neutrophils and other hematology parameters (hemoglobin and platelets) are at baseline concentration.
	> 30% ↓ from baseline	Neutrophils below reference range at baseline	Reduce dose to previous dose level if up-titration has occurred or reduce dose to 15 mg QOD if on 15 mg QD. No further dose ↑ until resolution of abnormality.	Weekly repeat testing	Not applicable.

Test	Result	Conditions	Action with ALXN1840 Dosing	Changes in Safety Monitoring ^a	Re-Challenge ^b
Bilirubin	> 2 × ULN	Accompanied by ALT > 3 × ULN, indicative of liver injury.	Temporary interruption	Weekly repeat testing	At 15 mg QOD or less frequent, when bilirubin is below ULN. Re-challenge under these conditions requires approval of the Alexion Medical Monitor.
UWDRS-III and clinical neurological assessment	Increase in UWDRS-III score from baseline as follows, AND is deemed clinically significant by the Investigator: Baseline UWDRS-III score < 20: ≥ 4-point increase OR Baseline UWDRS-III score ≥ 20: ≥ 6-point increase		Investigator and Alexion Medical Monitor will evaluate the need for dose modification (interruption, increase or decrease) based on Cu control parameters and relevant clinical data. Rationale for dosing decision must be documented in study record and re-evaluated at the next study visit.	Report neurologic adverse event of special interest and perform UWDRS Parts I, II and III. Re-evaluate neurologic status, including complete UWDRS examination, no later than next study visit, even if not planned per the SoA.	Discuss with the Alexion Medical Monitor.
Psychiatric assessment	Clinically significant signs of psychiatric worsening according to the BPRS		Investigator and Alexion Medical Monitor will evaluate the need for dose modification (interruption, increase or decrease) based on Cu control parameters and relevant clinical data. Rationale for dosing decision must be documented in study record and re-evaluated at the next study visit.	Re-evaluate psychiatric status no later than next study visit, even if not planned per the SoA.	Discuss with the Alexion Medical Monitor.

^a For changes in safety monitoring, weekly repeat testing for laboratory parameters may be completed by a home healthcare nurse, where applicable, if a routine study visit is not scheduled during this time period.

^b A maximum of 3 re-challenges will be allowed. For re-challenges, patients who were on 15 mg QOD should be re-challenged at the 15 mg QOD dose. The Investigator, in consultation with the Medical Monitor, may change dose and dose frequency in patients who require re-challenge.

Abbreviations: ALT = alanine aminotransferase; BPRS = Brief Psychiatric Rating Scale-24; Cu = copper; QD = once daily; QOD = every other day; SoA = Schedule of Activities; ULN = upper limit of normal; UWDRS = Unified Wilson Disease Rating Scale.

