1.3. Schedules of Activities

The Schedule of Activities (SoA) for the Screening and Treatment Periods is provided in [Table 1](#). In the Screening Period, the liver biopsy should be performed after all other screening activities have been completed, including imaging, and the patient has met all inclusion and no exclusion criteria.

The Day 337 (Week 48) visit is the end of the Treatment Period and the beginning of the Extension Period (ie, the Week 48 visit and the Extension Period Day 1 visit will occur on the same day). All assessments for the Week 48 visit and the liver biopsy must be performed before the first dose of ALXN1840 on Day 1 of the Extension Period. Dosing of ALXN1840 on Extension Period Day 1 marks the beginning of the Extension Period. Patients who do not enter the Extension Period will discontinue dosing at Week 48 following the second liver biopsy and will have a final study visit for safety follow up at Day 365 (Week 52) of the Treatment Period.

The SoA for the Extension Period is provided in [Table 2](#).

On study visit days where laboratory sampling is planned, patients will be asked to withhold any doses of ALXN1840 due to be taken prior to their visit, to allow laboratory samples to be taken pre-dose.

Laboratory specimen handling and processing instructions will be provided in the study laboratory manual. Blood samples should not be collected from a heparinized line.

Unscheduled visits that occur outside the protocol-specified visits are permitted at the discretion of the Investigator. Procedures, tests, and assessments conducted during unscheduled visits will be performed at the discretion of the Investigator.

Table 1: Schedule of Activities –Treatment Period

	Screening	Treatment Period													UNS ^a	Follow-Up ^b	
Day	-28 to -1	1 ^c	8 ^d	15 ^d	29 ^e	43 ^e	57 ^e	85 ^e	127 ^e	169 ^e	211 ^d	253 ^e	295 ^d	337 ^e / ET ^e		365	
Week	-4 to 0		1	2	4	6	8	12	18	24	30	36	42	48		52	
Window (days)			±3										±7	±3	±7		±7
Obtain informed consent (written or electronic)	X																
Review eligibility criteria	X ^f																
Medical history ^g and demographic parameters ^h	X																
WD medication history	X	X															
Physical examination	X													X		X	
Abbreviated physical examination ⁱ		X			X	X	X	X	X	X		X					
Vital signs ^j	X	X			X	X	X	X	X	X		X		X		X	
12-lead ECG	X					X								X			
FSH ^k	X																
HIV/hepatitis B and C testing	X																
DNA sample		X ^l															

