4.3. Justification for Dose

For this study, the term “dose” refers to the following:

Dosing for ALXN1840 will be initiated at 15 mg once daily, then the dose will be increased to 30 mg once daily at Week 6.

A starting dose of 15-60 mg daily was shown to have an acceptable safety profile and was effective in reducing NCC in a Phase 2 study in patients with WD (Weiss, 2017). Elevation of hepatic transaminases and/or gamma glutamyl transferase occurred in 39% of patients in the Phase 2 study and were generally associated with higher doses of ALXN1840. Elevations of

liver enzymes were detected by routine laboratory monitoring and were managed by dose reduction or treatment interruption of ALXN1840. In this study, the starting dose will be 15 mg once daily for the first 6 weeks, then the dose will be titrated up to 30 mg once daily. Elevation of liver enzymes, if occurring, and management of other laboratory abnormalities or AEs, will be managed according to [Table 6](#). Any change to dosing in response to laboratory results or AEs must be discussed with the Alexion Medical Monitor and documented in the study record. Subsequent dose increases must be approved by Alexion.

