8.2.4. Clinical Safety Laboratory Assessments

- See [Section 10.2](#) for the list of clinical laboratory tests to be performed and to the SoAs for the timing and frequency ([Table 1](#) and [Table 2](#)).
- The Investigator must review the laboratory report, document this review, and record any clinically relevant changes occurring during the study in the AE section of the CRF. The laboratory reports must be filed with the source documents. Clinically significant abnormal laboratory findings are those which are not associated with the underlying disease, unless judged by the Investigator to be more severe than expected for the patient's condition.
- All laboratory tests with values considered clinically significantly abnormal during participation in the study or within 4 weeks after the last dose of study drug should be repeated until the values return to normal or baseline or are no longer considered clinically significant by the Investigator or Alexion Medical Monitor.
 - If such values do not return to normal/baseline within a period of time judged reasonable by the Investigator, the etiology should be identified and Alexion notified.
 - All protocol-required laboratory assessments, as defined in [Section 10.2](#), must be conducted in accordance with the laboratory manual and the SoAs ([Table 1](#) and [Table 2](#)).
 - If laboratory values from non-protocol specified laboratory assessments performed at the institution's local laboratory require a change in patient management or are considered clinically significant by the Investigator (eg, SAE or AE or dose modification), then the results must be recorded in the CRF.

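### In Table 6 a fall in platelets from a within-range baseline triggers no dose reduction, weekly testing or hold on up-titration until 30,000/µL; neutrophils share the gap, but it may be small

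*Protocol*

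**What the plan says.** Protocol Section 6.6, Table 6, gives platelets and neutrophils two rows each.

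- **Interruption.** Platelets below 30,000/µL or neutrophils below 1.0 x 10^3/µL, whatever the baseline.
- **Reduction.** A fall of more than 30% from baseline leads to a lower dose, no further increase until the abnormality resolves, and weekly testing. The condition is "Platelets below reference range at baseline" for one count and "Neutrophils below reference range at baseline" for the other.

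Other tests in the table are built differently. ALT has one set of rows for patients above range at baseline and another headed "ALT within reference range at baseline". Both hemoglobin rows, the interruption row at "< 8 g/dL in the absence of bleeding" and the row for a fall of more than 30%, have no baseline condition. The triglyceride and cholesterol rows have none either.

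Section 6.6 also raises every patient from 15 mg to 30 mg once daily at Week 6. In Table 1 (Section 1.3), hematology after Day 1 is scheduled at Weeks 4, 6, 8, 12, 18, 24, 36 and 48. Table 3 (Section 2.3.1) lists leukopenia and bone marrow toxicity, attributed to overtreatment, as a risk. The mitigation given in that row is dose modification under Section 6.6 or discontinuation under Section 7.

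**The concern.** The dose reduction, the hold on up-titration and the weekly testing all sit in one row, so all three are lost when its baseline condition is not met. A patient whose platelets fall from 200,000 to 50,000/µL at Week 24 meets no platelet criterion in Table 6, and the next scheduled count is at Week 36. A patient who starts at 120,000/µL (below range on the assumed limits) is reduced and tested weekly once below 84,000/µL. So the rule acts at a lower count for the patient who has lost more. Likewise, a fall found at Week 4 from a within-range baseline places no hold on the Week 6 increase.

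At stake is early, uniform action on marrow suppression from copper depletion, a risk that the protocol names and leaves largely to Section 6.6 to manage.

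**Working it through.** The plan states no figure on this point, so the check is of the table's logic, followed by the size of the gap.

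**Inputs.** From Table 6: interruption at 30,000/µL (platelets) and 1.0 x 10^3/µL (neutrophils); reduction at 0.7 x baseline, below-range patients only. From Section 5.2, criterion 5: platelets under 100,000 are excluded. The documents give no reference ranges for these counts. The lower limits are therefore assumed: 130,000-150,000/µL for platelets and 1.5-2.0 x 10^3/µL for neutrophils.

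**Fall needed before any Table 6 action on that count, within-range baseline:** 1 - threshold/baseline.

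| Count | Baseline | Fall to first trigger |
|---|---|---|
| Platelets | 130,000 | 1 - 30/130 = 77% |
| Platelets | 150,000 | 1 - 30/150 = 80% |
| Platelets | 200,000 | 1 - 30/200 = 85% |
| Platelets | 250,000 | 1 - 30/250 = 88% |
| Neutrophils | 1.5 | 1 - 1.0/1.5 = 33% |
| Neutrophils | 2.0 | 1 - 1.0/2.0 = 50% |

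The example fall from 200,000 to 50,000/µL is 1 - 50/200 = 75%, still short of interruption.

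**Where the below-range row acts.** Platelets: from 0.7 x 100,000 = 70,000 (the entry floor) up to 0.7 x 130,000 = 91,000 or 0.7 x 150,000 = 105,000/µL, depending on the limit. Neutrophils: at most 0.7 x 1.5 = 1.05 or 0.7 x 2.0 = 1.40 x 10^3/µL. For neutrophil baselines below 1.0/0.7 = 1.43, interruption comes first and the reduction row adds nothing.

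**Spacing of scheduled counts after Week 24.** 253 - 169 = 84 days and 337 - 253 = 84 days. Table 1 has columns for Days 211 and 295 but marks no hematology there.

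**Trigger under the fix:** 0.7 x lower limit. Platelets: 91,000 (limit 130,000) or 105,000/µL (limit 150,000). From a baseline of 200,000 these are falls of 1 - 91/200 = 54.5% and 1 - 105/200 = 47.5%, against 85% now. Neutrophils: 1.05 (limit 1.5) or 1.40 (limit 2.0). At a baseline equal to the limit, the new row and the below-range row give the same trigger. The ALT rows join in the same way: 2 x ULN for within-range patients and 2 x baseline above range.

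**Cost to power, as an illustration.** Section 9.2 has n = 24, effect 228 and SD 319, with a paired t-test at one-sided 0.025. The noncentral t distribution gives 91.8%, which reproduces the stated 92%. Suppose k of 24 patients are reduced and each loses half the effect. The mean effect is then 228 x (1 - 0.5k/24).

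| k | Mean effect | Power |
|---|---|---|
| 0 | 228.0 | 91.8% |
| 1 | 223.25 | 90.7% |
| 2 | 218.5 | 89.5% |
| 3 | 213.75 | 88.2% |

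**The case against.** **Absence from Table 6 is not absence of action.** A reader might infer that a within-range patient with a steep fall would simply continue on full dose. The documents do not support that. Section 1.3 states: "Unscheduled visits that occur outside the protocol-specified visits are permitted at the discretion of the Investigator". Section 4.1 allows reduction or interruption for tolerability. Section 4.3 says: "Any change to dosing in response to laboratory results or AEs must be discussed with the Alexion Medical Monitor". Under Section 8.2.4, laboratory values judged clinically significant "should be repeated until the values return to normal or baseline" or until no longer considered significant. Section 7.1 has the investigator decide on management after a clinically significant finding, and Section 7.2 lists severe laboratory abnormality as a ground for discontinuation. Section 6.6 allows agreed deviations from the dose rules, and a data monitoring committee reviews safety (Section 9.5). The hemoglobin row may also catch the same patient. All this stands, and a fall to 50,000/µL would plausibly prompt action. But none of these provisions sets a platelet or neutrophil count, or a repeat interval.

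**The named risk and the large gap do not line up neatly.** Table 3 names leukopenia and bone marrow toxicity; it does not list low platelets separately. The large gap is in platelets, and the neutrophil gap may be slight. A reader might infer that both counts are equally affected. They are not, and the weight belongs on platelets.

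**The restriction may be deliberate.** A 30% fall from 400,000/µL leaves 280,000, which is unremarkable. A relative rule for patients already low, plus an absolute rule for all, is a coherent scheme. That is a good reason not to extend the 30% rule to everyone. It does not explain why nothing lies between a normal count and 30,000/µL.

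**Conclusion.** The gap is real and is a feature of the rule as written. For platelets it is large on any plausible lower limit: a within-range patient reaches the first platelet criterion only after a fall of at least 77-80%, while a below-range patient is reduced after 30%. For neutrophils it runs from almost nothing (1.0 against 1.05) to moderate (1.0 against 1.40), depending on the laboratory's limit.

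The row reading is certain. The sizes rest on assumed reference limits, because the documents give none. The documents do not show that harm is likely or how many patients would be affected, and discretionary safeguards remain. The change should be made, with platelets first.

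**What to change.** Add one row each for platelets and neutrophils within the reference range at baseline, following the ALT pattern. The trigger is a count more than 30% below the lower limit of the reference range: about 91,000-105,000/µL for platelets and 1.05-1.40 x 10^3/µL for neutrophils on the assumed limits. Apply the actions of the existing reduction row: weekly testing, no further increase until resolution, and the same dose reduction.

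With a platelet limit of 150,000/µL, the trigger of 105,000 lies slightly above the entry floor of 100,000. If the clinical team wants fewer reductions, it may choose a lower absolute platelet cut, provided that it is above 30,000/µL. If the present restriction is intended, give the reason in Section 6.6.

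The cost is amendment wording; the counts are already collected. The downside is a few more dose reductions and repeat counts, and re-escalation needs sponsor approval. The documents do not allow the number to be estimated. In the illustration above, 1 to 3 reduced patients of 24, each losing half the effect, would move power from 92% to 91-88%.

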6.7. Drug after the End of the Study

ALXN1840 will not be provided after the end of the 48-week Extension Period of the study.

7. DISCONTINUATION OF STUDY DRUG AND PATIENT DISCONTINUATION/WITHDRAWAL

7.1. Discontinuation of Study Drug

If it becomes necessary for a patient to permanently discontinue (definitive discontinuation) study drug, the patient must complete an Early Termination (ET) visit. See the SoAs ([Table 1](#) and [Table 2](#)) for data to be collected at the time of discontinuation of study drug and follow-up, and for any further evaluations that need to be completed.

Discontinuation of study drug for abnormal liver chemistry tests should be considered by the Investigator when a patient meets one of the conditions outlined in the Dose Modification criteria (see [Table 6](#)) or if the Investigator believes that it is in best interest of the patient.

If a clinically significant finding is identified (including suicidality) after enrollment, the Investigator or qualified designee will determine if the patient can continue in the study and if any change in patient management is needed. Any new clinically relevant finding should be reported as an AE.

For clinically significant findings from baseline in QT interval corrected using Bazett's formula (QTcB) or Fridericia's formula (QTcF), review of the ECG printed at the time of collection must be documented.

For details relating to pregnancy, see [Section 8.3.5](#) and [Section 10.4](#).

See the SoAs ([Table 1](#) and [Table 2](#)) for samples and data to be collected at the time of drug discontinuation and follow-up and for any further evaluations that need to be completed.

7.1.1. Temporary Discontinuation

Dose modification and reasons for interruption or discontinuation of dosing are detailed in [Section 6.6](#) for ALXN1840.

7.1.2. Rechallenge

See [Table 6](#) for details of rechallenge for ALXN1840.

7.2. Patient Discontinuation/Withdrawal from the Study

- A patient may withdraw from the study at any time at his/her own request or may be withdrawn at any time at the discretion of the Investigator for safety, behavioral, compliance, or administrative reasons. This is expected to be uncommon.
- At the time of discontinuing from the study, if possible, an ET visit should be conducted, as shown in the SoAs. See the SoAs for data to be collected at the time of study discontinuation and follow-up and for any further evaluations that need to be completed ([Table 1](#) and [Table 2](#)).
- The patient will be permanently discontinued both from the study drug and from the study at that time.

- If the patient withdraws consent for disclosure of future information, Alexion may retain and continue to use any data collected before such a withdrawal of consent.
- If a patient withdraws from the study, he/she may request destruction of any samples taken and not tested, and the Investigator must document this in the site study records.

Participation of a patient in this clinical study may be discontinued for any of the following reasons:

- The patient or/legal guardian withdraws consent or requests discontinuation from the study for any reason, is lost to follow-up or dies.
- Occurrence of any medical condition or circumstance that exposes the patient to substantial risk and/or does not allow the patient to adhere to the requirements of the protocol.
- Occurrence of a decompensated cirrhosis event which is not responsive to standard treatment.
 - A decompensation cirrhosis event is defined as acute esophageal or gastric variceal bleeding, development of new overt hepatic encephalopathy, or substantive *de novo* ascites formation.
- Any SAE, clinically significant AE, severe laboratory abnormality, intercurrent illness, or other medical condition which indicates to the Investigator that continued participation is not in the best interest of the patient.
- Patient becomes pregnant or is unwilling to comply with protocol requirements for highly effective contraception.
- Requirement to take prohibited concomitant medication or enroll in a clinical study of an experimental or unapproved/unlicensed therapy.
- Patient failure to comply with protocol requirements or study-related procedures.

